### 3.5.4. Electrocardiogram (ECG)

*Electrocardiograms (ECGs) should be collected at times specified in the Study Procedures (Section 6) of this protocol.*

*All scheduled ECGs should be performed after the subject has rested quietly for at least 10 minutes in a supine position.*

The average of the triplicate readings collected at each assessment time will be calculated prior to analyzing each ECG parameter. If more than three readings are collected at one triplicate ECG assessment time, average across all readings will be calculated. If any of the three individual ECG tracings has a QTc value  $\geq 500$  msec, but the mean of the triplicates is not  $\geq 500$  msec, the data from the subject's individual tracing will be described in a safety section of the study report in order to place the  $\geq 500$  msec value in appropriate clinical context. However, values from individual tracings within triplicate measurements that are  $\geq 500$  msec will not be included in the categorical analysis unless the average from the triplicate measurements is also  $\geq 500$  msec. The mean measurement is reported.

Baseline will be the average of the triplicate ECG measurements collected on Day -1/Rand. Change and percent change from baseline will be calculated at each time point for each ECG parameter.

If not supplied, QTcF will be derived using Fridericia's heart rate correction formula:

$$QTcF = QT / (RR)^{1/3} \quad \text{where } RR = 60 \text{ bpm/HR (if not provided)}$$

If QTcB is collected, then it should be listed only.

Determine if there are any ECG data abnormalities of potential clinical concern as defined in Pfizer Data Standards.

### 3.5.5. Physical Examination

Physical Examination will be measured at times specified in the STUDY PROCEDURES section of the protocol.

### 3.5.6. Neurological Examination

Neurological Examination will be measured at times specified in the STUDY PROCEDURES section of the protocol.

### 3.5.7. Columbia Suicide Severity Rating Scale (C-SSRS)

*The Columbia Suicide Severity Rating Scale (C-SSRS) is an interview based rating scale to systematically assess suicidal ideation and suicidal behavior. Versions are available for "lifetime" and "since last evaluation". The "lifetime" evaluation is done at screening, and the "since last evaluation" is done at all other time points. The C-SSRS is to be collected at times specified in the Study Procedures (Section 6) of this protocol by an appropriately trained clinical site staff member. The C-SSRS can also be administered at any time in the study at the discretion of the investigator based on any reasonable concern. At each suicidality assessment as per Study Procedures, subjects felt to have significant suicidal ideation with actual plan and intent or suicidal behavior, must be evaluated by a clinician/mental health professional (MHP) skilled in the evaluation of suicidality in the subjects by virtue of training or experience (eg, psychiatrist, licensed clinical psychologist) who will determine if it is safe for the subject to participate/continue in the trial. Specific criteria that indicate a need for such an assessment are:*

- *Suicidal ideation associated with actual intent and/or plan in the past 6 months; (a "YES" answer to C-SSRS questions 4 "some intent to act without specific plan" or 5 "specific plan and intent").*
- *Previous history of suicide behaviors in the past 5 years (a "YES" answer to any of the suicidal behavior items of the C-SSRS with the behavior occurring in the past 5 years).*

- *In the investigators judgment a risk assessment or exclusion is warranted. A written copy of the risk assessment should be included in the subject's clinical record (source documentation). Other possible suicidality adverse events or other clinical observations may, based on the judgment of the investigator, also trigger a risk assessment and require a narrative.*

*Suicidality adverse events or other clinical observations may, based on the judgment of the investigator and clinician/MHP, also trigger a risk assessment and a narrative using information from the C-SSRS, and available information, prior to screening and baseline information, and the clinician/MHP assessment. When there is a positive response to any question on the C-SSRS, the investigator should determine whether an adverse event has occurred.*

*At the baseline visits (Visit 1 (Randomization)), a risk assessment will be done by qualified staff at the clinical site to determine whether it is safe for the subject to be enrolled or to continue to participate in the trial.*

*Subjects who respond “YES” to items 4, 5 or to any behavioral question of the C-SSRS at any time after the baseline visit (Visit 1 (Randomization)) will be assessed by clinician/MHP to determine whether it is safe for the subject to continue in the trial.*

*Subjects who respond “YES” to items 4, 5 or to any behavioral question of the C-SSRS on more than one occasion during a trial must have their suicidality managed appropriately by the investigator together with the clinician/MHP (or the investigator alone if the investigator is a qualified mental health professional). Depending on the specifics of the subject as assessed by the investigator and/or clinician/MHP, the subject may be discontinued from the trial.*

C-SSRS responses will be mapped to the Columbia Classification Algorithm of Suicide Assessment (C-CASA).

**Table 3. C-SSRS Mapped to C-CASA - Suicidality Events and Codes**

C-CASA Event Code	C-CASA Event	C-SSRS Response
1	Completed suicide	As captured in the safety database
2	Suicide attempt	“Yes” on “Actual Attempt”
3	Preparatory acts towards imminent suicidal behavior	“Yes” on any of the following: 
 
• ”Aborted attempt”, or
 
• “Interrupted attempt”, or
 
• “Preparatory Acts or Behavior”
 

C-CASA Event Code	C-CASA Event	C-SSRS Response
4	Suicidal ideation	“Yes” on any of the following: 
 
• “Wish to be dead”, or
 
• “Non-Specific Active Suicidal Thoughts”, or
 
• “Active Suicidal Ideation with Any Methods (Not Plan) without Intent to Act”, or
 
• “Active Suicidal Ideation with Some Intent to Act, without Specific Plan”, or
 
• “Active Suicidal Ideation with Specific Plan and Intent”
 

7	Self-injurious behavior, no suicidal intent	“Yes” on “Has subject engaged in Non-suicidal Self-Injurious Behavior?”

The following 3 endpoints are key endpoints for suicidality data analysis and evaluation:

- Suicidal Behavior;
- Suicidal Ideation;
- Suicidal Behavior or Ideation.

Suicidal behavior: A subject is said to have suicidal behavior if the subject has experienced any of the following events (C-CASA event codes 1-3):

- Completed suicide;
- Suicide attempt; or
- Preparatory acts toward imminent suicidal behavior.

Suicidal ideation: Any observed suicidal ideation maps to a single C-CASA category. Depending on the scale used, more granularity of observed ideation (sub-categories of C-CASA category 4) may be displayed. The C-SSRS, for example, includes five ideation questions (that map to C-CASA category 4) with increasing severity.

Subjects with new onset suicidality: A subject will be considered to have a new onset of suicidality if the subject reported no ideation and no behavior at the baseline assessment (note that self-injurious behavior, no suicidal intent [C-CASA code 7] is not considered to be suicidal ideation or behavior) and reported any behavior or ideation post-baseline. Data observed at screening is not considered in the definition of new onset.

Subjects with worsening suicidality relative to baseline: A subject will be considered to have a worsening of suicidality if the subject moved to a lower numbered C-CASA category (observed in categories 1-4) than was reported at baseline. Movement within C-CASA categories 5-9 would not be considered worsening. In addition, worsening will be considered within the suicide ideation C-CASA category 4 if there is an increase in severity identified in the C-SSRS which captures additional granularity on suicide ideation. A subject who reports only ideation at baseline and who reports any behavior post-baseline is considered to have worsened. Data observed at screening is not considered in the definition of worsening.

Table 4. C-SSRS Mapped to C-CASA – Examples of Worsening/New Onset shows examples of new onset suicidality and worsening suicidality for C-SSRS after mapping to C-CASA.

**Table 4. C-SSRS Mapped to C-CASA – Examples of Worsening/New Onset**

New Onset		Worsening	
Baseline	Any post-baseline (or by Week)	Baseline	Any post-baseline (or by Week)
No ideation and no behavior	C-CASA code=4 (any ideation) or C-CASA code=1, 2, or 3 (any behavior)	Only C-CASA code=4 (Ideation only)	C-CASA code=3, 2, or 1 (any behavior)
		Lowest C-CASA code=4	C-CASA code=3, 2, or 1 (any behavior)
		Lowest C-CASA code=3	C-CASA code=2, or 1
		Lowest C-CASA code=2	C-CASA code=1

With the C-SSRS, worsening may also be observed within suicidal ideation. In this case, the order of suicidal ideations with increasing worsening is as follows: wish to be dead, non-specific active suicidal thoughts, active suicidal ideation with any methods (not plan) without intent to act, active suicidal ideation with some intent to act, without specific plan, and active suicidal ideation with specific plan and intent. All of these values will be considered worsening for reporting.

**3.5.8. Questionnaire for Impulsive-Compulsive Disorders in Parkinson’s Disease – Rating Scale (QUIP-RS)**

*The Questionnaire for Impulsive-Compulsive Disorders in Parkinson’s Disease – Rating Scale (QUIP-RS) is a PD-specific PRO designed to assess the severity of impulse control disorders in Parkinson’s disease. The estimated timeframe for completion is approximately 5 minutes.*

*The QUIP-RS has 4 primary questions pertaining to commonly reported thoughts, urges/desires, and behaviors associated with impulsive-compulsive disorder, each applied to the 4 impulsive-compulsive disorders (compulsive gambling, buying, eating, and sexual behavior) and 3 related disorders (medication use, punning, and hobbyism). It uses a 5-point Likert scale (score 0–4 for each question) to gauge the frequency of behaviors, and instructs patients to answer questions based on behaviors that occurred in the preceding 4 weeks (or any 4-week period in a designated time frame). The QUIP-RS is valid and reliable as a rating scale for impulse control disorders and related disorders in Parkinson’s disease, and can be used to support a diagnosis of these disorders, as well as to monitor changes in symptom severity over time.*

Each question is anchored with the following five responses: Never (0), Rarely (1), Sometimes (2), Often (3), and Very Often (4). The scoring range for each item (ie, disorder) is 0-16. If a subject has one to three missing items for an impulsive-compulsive disorder, the values for that disorder from their previous assessment will be carried forward and utilized; otherwise if the subject is missing all items for a disorder the score will be considered missing. The higher score indicates a greater level of the Impulsive-Compulsive Disorder.

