### 3. ENDPOINTS AND BASELINE VARIABLES: DEFINITIONS AND CONVENTIONS

#### 3.1. Primary Endpoint(s)

*Change from baseline in the Modified Unified Parkinson’s Disease Rating Scale (MDS-UPDRS) Score Part III at Week 15.*

MDS-UPDRS Part III assesses the motor signs of Parkinson’s disease and is administered by the investigator. It is comprised of 33 sub-scores based on 18 items, several with right, left or other body distribution scores. Each question is anchored with five responses that are linked to commonly accepted clinical terms: 0 = normal, 1 = slight, 2 = mild, 3 = moderate, and 4 = severe. Assessments will be done at times specified in the STUDY PROCEDURES section of the protocol. Higher total scores indicate more severe motor signs of Parkinson’s disease.

If more than 7 of the MDS-UPDRS Part III items are missing for a time point, the total score for that time point is missing; otherwise, the total score will be imputed as follows: sum of the non-missing item scores X (total number of items)/ (number of items non-missing).

Baseline will be the Day -1/Rand measurement.

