### **3.5.9. Physician Withdrawal Checklist (PWC-20)**

*The PWC-20 is a 20-item reliable and sensitive instrument for the assessment of BZ-like discontinuation symptoms. It correlates extremely highly with the PWC-35, its parent scale ( $r=0.980$ ). Since most items are also complaints commonly reported by patients as symptoms of anxiety, it is not surprising that the PWC-20 and the Hamilton Anxiety Rating Scale (HAM-A) correlate highly ( $r=0.80$ ) with each other. Therefore, a combination of symptoms and time course, not type of symptoms alone, best differentiate between discontinuation symptoms of rebound/withdrawal and return of anxiety. Discontinuation symptoms occur early and disappear rather swiftly, depending upon speed of taper, daily medication dose, and drug elimination half-life.*

Determine the number of subjects with each symptom present (eg, mild or higher severity) and categorize each subject by severity (eg, mild, moderate, and severe). Only non-missing items are considered in summary presentations, and will establish the denominator.

The total PWC-20 score is the sum of 20 item-scores and ranges between 0 and 60. The higher score indicates more frequent/severe symptoms. If more than 5 of the 20 individual items are missing then the total PWC-20 score will be set to missing; otherwise, the total PWC-20 score will be imputed as follows: sum of the non-missing item scores X (total number of items)/ (number of items non-missing).

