### 5.3. Methods to Manage Missing Data

For the analysis of safety endpoints, the sponsor data standard rules for imputation will be applied (eg, partial dates for AEs and concomitant medications will be imputed according to Pfizer standard algorithms).

For scales used in this study, scores will be imputed according to the imputation rules and algorithms for missing component scores that are provided in the data standard documents, or scale documentation. Details are included for each endpoint in [Section 3](#).

If baseline measures are missing, the last values prior to study treatment, provided that the data is collected on or after the screening visit will be used. This information is used as a reference for the measurements and observations made subsequent to the start of study treatment.

CCI [REDACTED]

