#### **6.6.8. Questionnaire for Impulsive-Compulsive Disorders in Parkinson's Disease – Rating Scale (QUIP-RS)**

For each planned time point and item (ie, disorder), baseline values, raw values and change from baseline values within each treatment will be summarized with descriptive statistics.

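### QUIP-RS: a partly answered disorder takes its values from the previous visit, which on the plain reading discards current answers and cannot work at baseline

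*SAP*

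**What the plan says.** SAP 3.5.8 describes four questions, each scored 0 to 4, asked about four impulsive-compulsive disorders and three related ones, with a score of 0 to 16 for each. The missing-data rule has two parts:

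- With one to three of a disorder's four questions unanswered, "the values for that disorder from their previous assessment will be carried forward and utilized".
- With none of the four answered, nothing is brought over from an earlier visit: "if the subject is missing all items for a disorder the score will be considered missing".

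The same section says the form "instructs patients to answer questions based on behaviors that occurred in the preceding 4 weeks", and adds in brackets that another 4-week period within a set time frame may be used. The protocol's Schedule of Activities places QUIP-RS at Visits 1, 6, 10 and 14, with none at Screening. SAP 6.6.8 summarizes the result descriptively: "For each planned time point and item (ie, disorder), baseline values, raw values and change from baseline values".

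SAP 5.3 refers to scale and data-standard documents and says the details for each endpoint are in SAP Section 3. Its fallback for a missing baseline is that "the last values prior to study treatment, provided that the data is collected on or after the screening visit will be used".

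**The concern.** What is carried forward is the disorder's values, not the values of the missing questions. On that reading a subject who answers three of four questions has those answers overwritten, while a subject who answers none is left missing. Current data are overridden only when they exist.

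The plural in the rule, and its trigger of missing items, also allow a narrower reading in which only the blank questions are filled. The section adds to the doubt by using the word item for a question in one sentence and for a disorder in the next. Nothing in SAP 3.5.8, 5.3 or 6.6.8 settles it, so two programmers could derive different scores from the same form.

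The choice affects a listed safety endpoint. A carried value pulls the score toward the past: it can hide behaviour that has newly emerged and can retain behaviour that has resolved. The SAP's other visible rules for partial forms do not do this. MDS-UPDRS Part III (SAP 3.1, "If more than 7 of the MDS-UPDRS Part III items are missing for a time point") and PWC-20 (SAP 3.5.9, "If more than 5 of the 20 individual items are missing then the total PWC-20 score will be set to missing") each set the total to missing beyond a limit and otherwise prorate from answers given at that visit.

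**Working it through.** **Inputs.** Scoring and rule: SAP 3.5.8. Visit days and windows: protocol Schedule of Activities. Dose stages, and Day 1 as the day after Visit 1: Table 2. Arm size of 44 and the 23% allowance: protocol 9.1. The documents give no rate of unanswered questions, so that rate is assumed below.

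**Score range.** 4 questions × 4 points = 16, which reproduces the SAP's 0–16.

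**What is carried, and from when.** The look-back is 28 days.

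| Visit scored | Source | Planned gap (days) | Gap within windows (days) | Consequence on the plain reading |
|---|---|---|---|---|
| 1 | none | – | – | rule cannot be applied |
| 6 (Day 35) | Visit 1 | 35 | 35–38 | pre-dose score; change from baseline is 0 |
| 10 (Day 63) | Visit 6 | 28 | 22–31 | possibly a lower titration dose |
| 14 (Day 105) | Visit 10 | 42 | 36–45 | older score, normally at the same dose |

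At planned timing no carried score shares a day with the current look-back. Within the windows, Visits 6 and 10 can overlap by at most 28 − 22 = 6 days. For a subject who follows Table 2 without delay, the Visit 6 look-back (Days 8–35) covers Stages 2–5 (0.75–5 mg) and the Visit 10 look-back (Days 36–63) covers Stages 6–8 (7–15 mg). Visit 14 also serves as the early termination visit, in which case its gap and source dose vary.

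**Baseline.** A partly answered disorder at Visit 1 has no earlier QUIP-RS, and the SAP 5.3 fallback has no screening value to draw on. The three later changes from baseline for that disorder are then undefined.

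**Scores under each reading** (hypothetical answers; – is unanswered).

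| Previous | Current | Whole disorder carried | Only blanks filled | Prorated | Possible true score |
|---|---|---|---|---|---|
| 0,0,0,0 | 4,4,4,– | 0 | 12 | 16 | 12–16 |
| 0,0,0,0 | 3,3,3,– | 0 | 9 | 12 | 9–13 |
| 4,4,4,4 | 0,0,0,– | 16 | 4 | 0 | 0–4 |

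The two readings differ by the change in the sum of the answered questions. The largest difference is 3 × 4 = 12, 2 × 4 = 8 or 1 × 4 = 4 points with one, two or three questions missing.

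**General bounds with three answers summing to s.** The true score lies in [s, s + 4]. The prorated score is 4s/3 = s + s/3. Since 0 ≤ s/3 ≤ 4, it is always inside that range and so is never wrong by more than 4. A carried 0 is inside only when s = 0, so it is impossible for 5³ − 1 = 124 of the 125 answer patterns. This counts patterns and is not a probability. In the first row the carried score is wrong by 12 to 16.

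**Effect on an arm mean.** One such subject among 44: 12/44 = 0.27 to 16/44 = 0.36 points.

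**Frequency, under an assumption.** If each question is skipped independently with probability q, then P(1 to 3 of 4 missing) = 1 − (1 − q)⁴ − q⁴. Post-baseline scores per arm if all complete: 44 × 7 disorders × 3 visits = 924.

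| q (assumed) | Share affected | Scores of 924 |
|---|---|---|
| 0.5% | 1.99% | 18 |
| 1% | 3.94% | 36 |
| 2% | 7.76% | 72 |
| 5% | 18.55% | 171 |

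If only 34 per arm contributed (44 × 0.77 = 33.9), there would be 34 × 7 × 3 = 714 scores, with 14, 28, 55 and 132 affected.

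**The case against.** The strongest reply is that filling only the blank questions is a natural reading. It keeps current answers, does not by itself force change from baseline to 0, and in the tabulated examples gives scores inside the possible range. On that view the sentence needs clarifying, not replacing. This stands in part: the worst figures above belong to the plain reading. But the narrower reading still adds an earlier period's answers to current ones, and still gives nothing at Visit 1.

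The size is also uncertain. The 124 of 125 count gives every answer pattern equal weight, and the documents give no QUIP-RS distribution. The frequencies rest on an assumed, independent skip rate. If subjects tend to skip whole disorders, all four answers are missing and the rule never applies, so the counts would be lower. These limits stand. So does the bracketed alternative to the preceding 4 weeks: the non-overlap argument assumes the usual look-back.

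QUIP-RS carries no test or decision rule. The data are reviewed during the study (protocol 9.4), adverse events are assessed at every visit, and an external committee reviews unblinded safety data (protocol 9.6). A problem is therefore unlikely to go unseen because of this rule alone.

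Finally, SAP Appendix 2 and the scale documentation cannot be seen, and only two comparison rules are visible, both for longer scales. That limits the inconsistency argument. However, SAP 5.3 says the details are in Section 3, and that text is visible.

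**Conclusion.** The concern holds. As written, the rule can report a score that the subject's own answers at that visit rule out. It has two defensible readings up to 12 points apart, and it has no answer at baseline. The two-reading problem and the baseline gap follow from the text and the visit schedule. The overwriting of current answers depends on the plain reading.

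The consequence is moderate. It is limited to the descriptive by-disorder summaries, where one extreme subject moves an arm mean by about 0.3 points. The number of affected scores is unknown, and the 2.0%–18.5% range depends wholly on the assumed skip rates and on independence between questions. The primary endpoint and the sample size are not touched. The rule should still be changed, because it is wrong in kind for a safety scale and cheap to correct.

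**What to change.** Replace the rule in SAP 3.5.8 with one that uses only current-visit answers, for example:

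*For each of the seven disorders, when three or four of the four questions are answered at a visit, the score is four times the mean of the answered questions. With fewer than three answers the score is missing. Nothing is carried forward. Every partly answered disorder is listed with its responses.*

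Apply it at all visits, including Visit 1. The minimum of three in four (75%) matches the PWC-20 rule, which allows at most 5 of 20 items missing.

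The cost is one sentence, one derivation line and one listing. Proration assumes the unanswered question resembles the three answered ones, gives some fractional scores, and lets each answer carry a third of the result. Disorders with only one or two answers drop out of the summary but stay in the listing. From 6q²(1 − q)² + 4q³(1 − q), that is about 0.1 of 924 scores per arm at q = 0.5% and 13 at q = 5%. If the sponsor prefers carry-forward, the SAP must at least state whether it applies to the blank questions or the whole disorder, and what happens at Visit 1.
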